9.3 VARIABLES

9.3.1 Exposures

The primary exposure of interest is treatment with afatinib. Two cohorts of patients will be created: the afatinib-treated cohort includes patients with an *NRG1* gene fusion-positive solid tumor who had received afatinib in any line of therapy; the second cohort includes patients with an *NRG1* gene fusion-positive solid tumor who had not received afatinib prior to the date of data collection. Patients treated with afatinib monotherapy and their outcomes will be described in addition to the two main aforementioned treatment groups.

9.3.2 Outcomes

Demographic and clinical characteristics of patients with *NRG1* gene fusion-positive solid tumors treated with afatinib and of patients with *NRG1* gene fusion-positive solid tumors treated with other systemic therapy will be summarized for each cohort. These variables serve as outcomes in terms of fulfilling study objectives. These variables also serve as covariates to contextualize other study outcomes (e.g., ORR, DOR, DOCB, PFS, TOT, TTP, OS, AEs).

Table 1. Patient demographics and clinical characteristics.

Characteristic	Definition
Sex	Patient sex, as charted
Age(s)	Age at diagnosis of solid tumor and age at initiation of afatinib or other systemic therapy
Region	US census region of patient: Northeast, South, Midwest, West
Race/ethnicity	Race and ethnicity of patient, as charted
Tumor type	Description/classification of primary tumor of patient (e.g., NSCLC, cholangiocarcinoma, pancreatic cancer)
ECOG PS	ECOG PS of patient at initiation of afatinib or other systemic therapy
Comorbidities	Comorbidities present at initiation of afatinib or other systemic therapy, following Charlson comorbidity index
Stage	Stage of tumor at initiation of afatinib or other systemic therapy
NRG1 results	Date of NRG1 gene fusion test; laboratory performing test (e.g., academic, reference, in-house lab; name of lab); NRG1 gene fusion partner
Other biomarkers	Tumor-specific biomarkers tested and their results (e.g., MSI/MMR, EGFR, HER2)

The ORR among patients with *NRG1* gene fusion-positive solid tumors treated with afatinib and among patients with *NRG1* gene fusion-positive solid tumors treated with other systemic therapy will be calculated as the proportion of patients with a complete response (CR) or partial response (PR) out of all patients (CR+PR/all patients) (see **Table 2** below). Disease response for determining the ORR will be reported as recorded in the patient's EHR, including the date of radiographic imaging used to substantiate the patient's initial and best response to therapy. Providers will indicate whether the patient experienced a CR, PR, stable disease (SD), or progressive disease (PD). No independent blinded review of radiology studies will be conducted. Lesion measurements at baseline (initiation of afatinib; initiation of other systemic therapy for non-afatinib treated patients), initial response, and best response will be abstracted as available. Changes in the number, locations, and sizes of lesions at initial and best response to therapy will be evaluated by [REDACTED] using RECIST v1.1 guidelines. The sum of lesion measurements will be assessed at baseline and at follow-up scans to calculate the percent change in sum of target lesions, as well as account for new lesions on follow-up scan in order to classify response by RECIST v1.1 criteria. Actual scan images will not be reviewed; the calculation of real-world disease response will be based on the lesion measurements provided. Other outcomes include PFS, TOT, TTP, OS, DOR, DOCB, AEs. Definitions of these outcomes are shown in **Table 2**.

Table 2. Study outcomes and definitions.

Outcome	Definition
ORR	Proportion of patients with a complete response (CR) or partial response (PR) out of all patients (CR+PR/all patients) at initial response assessment and best response
DOCB	Duration of clinical benefit (DOCB) will be calculated as the time from initial response (for any patient with a complete, partial, or stable disease response initially) until the earliest of either disease progression or death. Patients who discontinue therapy due to a reason other than progression will be censored on the date of discontinuation. Patients still on therapy at the time of data cut-off will be censored on their last visit date.
DOR	Duration of response will be calculated as the time from initial response (for any patient with a complete or partial response initially) until the earliest of either disease progression or death. Patients who discontinue therapy due to a reason other than progression will be censored on the date of discontinuation. Patients still on therapy at the time of data cut-off will be censored on their last visit date.
TOT	Time from initiation of a line of therapy until discontinuation for any reason; patients on therapy at the time of data cut-off will be censored on the last date of treatment.
TTP	Time from initiation of a line of therapy until discontinuation due to disease progression; patients on therapy or those who discontinued due to a reason other than disease progression will be censored on the last date of treatment.

PFS	Time from initiation of a line of therapy until disease progression or death; patients on therapy at the time of data cut-off will be censored on the last date of treatment. Patients who discontinue a line of therapy for a reason other than disease progression but who subsequently die prior to the receipt of any other therapy will be considered an event on the date of death.
OS	Time from initiation of any therapy in the metastatic setting until death; patients alive at the time of data cut-off will be censored on the last date the patient was seen by the provider/clinic.
AE	An adverse event is defined as any untoward medical occurrence in a patient administered a medicinal product and which does not necessarily have a causal relationship with this treatment. AEs from a prepopulated list (including “other, please specify”) during each line of therapy will be indicated by providers. The number and proportion of patients experiencing each AE reported during afatinib or other systemic therapy will be reported. See Section 11.1 and Table 3 for further details.

In addition to TOT, to further characterize treatment patterns for those treated with afatinib and those treated with other systemic therapy, the following will be collected (and calculated based on the collected data):

- Treatment history (i.e., regimens, duration, number of cycles, sequence)
- Starting dose of afatinib or other systemic therapy
- Dose modifications of afatinib or other systemic therapy (i.e., dose reductions and their timing, dose increases and their timing, dose delays and their duration and timing)
- Rationale for afatinib or other systemic therapy discontinuation

AEs will be collected and analyzed in the Clinical Study Report. Providers will be shown information describing what constitutes an AE/ADR/SAE/FAE per BI policies. The processes for safety reporting and analysis of the safety data will be implemented and conducted as per the BI non-interventional study (NIS) standard operating procedures. [REDACTED] will complete any reporting of events to BI per event reporting protocols.

The diagnosis, time, attribution (treatment-related or not per provider interpretation) and severity of the reported AEs during index therapy will be collected. If death is cited as rationale for discontinuation then provider will abstract data related to date of death, cause of death.

Table 3. Adverse events data collection.

Variable	Definition / response options
AEs during a given line of therapy	During each line of therapy, providers will indicate the AE that occurred including severity.
Start date of AE	Date each AE occurred

Severity (see section 11.1)	
Severity of each AE, as assessed by the provider, provided the following guidance:
 
 • Mild (mild symptoms; clinical or diagnostic observations only [e.g. lab work]; intervention not performed) • Moderate (minimal, local or noninvasive intervention performed [e.g., administration of fluids]) • Severe (medically significant ranging from not immediately life-threatening, life-threatening consequences, to death related to AE; [e.g., extensive monitoring, hospitalization or prolongation of hospitalization])
Resolution	
Outcome of each AE will be collected as:
 
 • Recovered/Resolved • Recovered/Resolved with sequelae • Not yet recovered/Not yet resolved • Fatal • Unknown
Outcome	
For all AEs, the outcome of the AE, regardless of severity indicated, will be assessed by participating providers. These outcomes will allow for the classification of serious and fatal AEs as defined in Section 11
 
 • Dose reduction • Dose hold/dose delay/schedule change • Discontinuation of treatment • Unscheduled office visit/treatment • Resulting in death • Life-threatening • Required inpatient hospitalization • Resulted in persistent or significant disability • Prolonged existing hospitalization
End date of AE	Date AE resolved/patient recovered (if resolved/recovered)
Causal relationship of AE to treatment	See section 11.2 for guidance on assessing causal relationship (i.e., afatinib or other systemic therapy)

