9.2.1 Provider/Site/Patient Selection

Provider Eligibility

Providers who meet the following criteria will be eligible to participate:

- 1) Are board-certified oncologist/hematologist.
- 2) Have treated/are treating at least one eligible patient with an *NRG1* fusion-positive solid tumor.
- 3) Are able to participate in research approved by an external institutional review board (IRB).
- 4) Agree to participate in data quality assurance/control processes.

Providers will select patients meeting the study eligibility criteria as described below. Providers will be asked to select eligible patients chronologically, starting with the first patient who first initiated any line of afatinib or chemotherapy, on or after 01/01/2017 through 03/31/2020.

Patient Eligibility

Inclusion Criteria:

- Adults, 18 years of age or older, at the time of diagnosis with any solid tumor.
- Confirmed *NRG1* gene fusion in any solid tumor.
- Initiated afatinib or other systemic therapy (in any line of therapy) for treatment of a solid tumor with *NRG1* gene fusion on or after 01/01/2017 through 03/31/2020.

- Followed up for ≥ 3 months after initiation of afatinib or other systemic therapy (unless deceased prior to 3 months of follow-up).

Exclusion Criteria:

- Treatment with any TKI/ErbB-directed therapy other than afatinib

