9.7 DATA ANALYSIS

Demographic and clinical characteristics will be reported by descriptive analyses including counts and frequencies for dichotomous and categorical variables, while measures of centrality (mean, median) and spread (min, max, standard deviation, interquartile range, as appropriate) will be used for continuous variables. These characteristics will be described at the time of initial diagnosis of advanced/metastatic disease and at the time of initiation of each line of therapy received, for the afatinib cohort and separately for the other systemic therapy cohort. No statistical comparisons will be made across these two cohorts in terms of demographic, clinical characteristics, and clinical outcomes.

The calculations for all outcomes (e.g., ORR, DOR, DOCB, TOT, TTP, PFS, OS) are defined in **Table 2** in Section **9.3.2 Outcomes**. For disease response, the point estimate for ORR and associated 95% confidence interval (CI) will be calculated for initial response to index therapy (i.e., afatinib or other systemic therapy) and best response to index therapy, for each cohort. ORR will be reported among subgroups within each of the treatment cohorts, by tumor type and line of therapy. The Kaplan-Meier method will be used to estimate time-to-event outcomes (DOR, DOCB, TOT, TTP, PFS, and OS) to account for any right-censoring (e.g., patient had not discontinued therapy, patient had not progressed, or died). Time-to-event outcomes will be described for each of the two treatment cohorts and in subgroups within the two treatment cohorts, according to solid tumor and line of therapy. All study outcomes will be reported separately for those treated with afatinib monotherapy. In the event an outcome cannot be assessed for a given patient, that patient would be omitted from assessment of that outcome; reason for omission in a given outcome assessment will be reported.

Cumulative incidence, severity, and timing of AEs during the index therapy will be summarized and displayed in number/percentage form for each of the treatment cohorts, separately. All safety endpoints will be analyzed descriptively. AE reporting is summarized in Section **11 Management and Reporting of Adverse Events/Adverse Reactions**.

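### Measurable disease at index is not recorded, so the lesion-sum ORR cannot separate patients who could not show a partial response from those whose lesions were not charted

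*Combined protocol and SAP*

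**What the plan says.** **Denominator.** Table 2 in Section 9.3.2 defines ORR as the proportion with CR or PR "out of all patients (CR+PR/all patients) at initial response assessment and best response". Section 9.7 then adds: "In the event an outcome cannot be assessed for a given patient, that patient would be omitted from assessment of that outcome", with the reason reported.

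**Response source.** Section 9.3.2 gives two. First: "Disease response for determining the ORR will be reported as recorded in the patient's EHR", with the provider choosing CR, PR, SD or PD. Second, lesion measurements are summed at baseline and follow-up "to calculate the percent change in sum of target lesions, as well as account for new lesions on follow-up scan in order to classify response" under RECIST v1.1. Images are not reviewed, and "the calculation of real-world disease response will be based on the lesion measurements provided". Nothing says which source fills the ORR numerator when the two differ or when measurements are absent.

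**Lesion data.** Measurements at baseline, "initial response, and best response will be abstracted as available". Section 9.4 makes only the eligibility elements compulsory and lets the rest be missing.

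**Population.** Section 9.2.1 asks for an adult with a confirmed fusion in any solid tumor who "Initiated afatinib or other systemic therapy (in any line of therapy) for treatment of a solid tumor with" that fusion within the index window, with at least 3 months of follow-up unless deceased. Measurable disease is not a criterion. Table 1 lists stage but has no item for measurable disease.

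**The concern.** Percent change in a lesion sum needs a baseline sum above zero. A patient with active but non-measurable disease at index is eligible, can be scanned and can progress, yet the lesion-sum calculation cannot give that patient a partial response. In the eCRF this patient looks the same as one who had a measurable lesion that nobody wrote down: both have a blank baseline.

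Section 9.7 plans ORR by cohort, tumor type and line of therapy. The second cohort is there to give context, and Section 7 says the data may support label expansion requests. If the share of patients with measurable disease varies across those groups, part of any difference in measurement-based ORR would reflect that share and not response. No source documents are supplied and no images are read, so the question could not be settled from the study data afterwards.

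**Working it through.** **Inputs from the documents.** Cohort targets of up to 70 and up to 50 (Section 9.5); ORR over all patients (Table 2); omission of patients who cannot be assessed (Section 9.7); 95% CI for ORR (Section 9.7).

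**Inputs assumed, because the documents give none.** r = ORR among patients with measurable disease, 20% to 50%. u = share without measurable disease, 10% to 30%.

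**Step 1: the plan's own precision figure.** Table 4 gives ±10.7% at a proportion of 30% and n = 70, labelled SE. The SE is √(0.30 × 0.70 / 70) = 5.48%, and 1.96 × 5.48% = 10.74%. The figure therefore reproduces as a 95% half-width, and it is used that way below.

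**Step 2: all patients kept in the denominator.** If patients without measurable disease contribute no CR or PR, the lesion-sum ORR is r × (1 − u), a loss of r × u points whatever the cohort size.

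| r | u = 10% | u = 20% | u = 30% |
|---|---|---|---|
| 20% | 18% | 16% | 14% |
| 30% | 27% | 24% | 21% |
| 40% | 36% | 32% | 28% |
| 50% | 45% | 40% | 35% |

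The loss runs from 2 points (20% × 10%) to 15 points (50% × 30%). Each value is an upper bound for its r and u, because a patient without measurable disease may still be classed as CR if all disease disappears.

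**Step 3: omission rule applied.** At r = 30%, u = 20% and n = 70, 14 patients leave and 56 remain. ORR is 30%, against 24% in Step 2. The same data give two answers up to 6 points apart, depending on which section is followed.

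**Step 4: why the data cannot resolve it.** Let w be the share with measurable disease whose sizes were not charted. Lesion sums exist for 1 − u − w of patients. The data set shows u + w but not u and w separately. Omission then drops both groups together, while keeping everyone counts both as non-responders on the lesion-sum measure.

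**Step 5: precision of a measurable-only ORR.** At r = 30% with 56 of 70 measurable: 1.96 × √(0.21 / 56) = 12.0 points, against 10.7. With 40 of 50 measurable: 1.96 × √(0.21 / 40) = 14.2 points, against 12.7.

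**The case against.** The strongest reply is that the planned ORR does not depend on the lesion sum. Section 9.3.2 says the response that determines ORR is the one in the health record, so a patient with no lesion sum can still be counted as CR or PR. This stands. A reader might infer that the protocol's ORR will be diluted by the factor 1 − u, but the documents do not support that. The loss applies only to an ORR built from measurements, and only as an upper bound.

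Second, Section 9.7 may remove these patients, and then there is no dilution. This also stands as a possible reading. It is not a dependable remedy, because these patients can be scanned and can show CR or PD, so it is unclear that they count as not assessable, and omission contradicts the all-patients definition. Reporting reasons for omission helps only if the eCRF captures why a baseline is blank.

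Third, baseline lesion sizes are abstracted where charted, so it would be wrong to say that nothing about measurable disease is collected. What is missing is a field that gives a blank its meaning.

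Fourth, the study is descriptive, no cohort comparison is planned, and an all-patient denominator is a recognised conservative choice. That limits the consequences. It does not settle which source or which denominator is used.

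**Conclusion.** The point holds in a limited form. ORR has two response sources without a hierarchy and two denominator rules that conflict, and measurable disease at index is neither required nor explicitly recorded. The measurement-based ORR is therefore either lowered by up to r × u points (up to 6 at r = 30% and u = 20%) or computed after dropping a group that mixes non-measurable with uncharted patients. Both r and u are assumptions, so the true size is unknown.

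A reader might also infer that tumor types, lines or cohorts will differ in measurable disease. The documents give no figures on this; it is a possibility that the plan leaves unchecked. The change is worth making because it is cheap and cannot be recovered once data collection closes.

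**What to change.** 1. Add a required eCRF item to Table 1: at least one measurable lesion on the last scan before index therapy (yes / no / no scan or unknown). Extend the Section 9.4 statement on required elements to cover it.
2. In Section 9.7, keep the all-patient ORR and add ORR with 95% CI among patients with measurable disease at baseline, per cohort and for the planned tumor-type and line subgroups.
3. Limit the lesion-sum recalculation to that set. Classify the others as CR, non-CR/non-PD, or PD.
4. State in Section 9.3.2 which response source fills the ORR numerator.
5. Align the Section 9.7 omission rule with the all-patients denominator in Table 2.

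The cost is one eCRF item, one further ORR row per table and a few sentences of text. The added estimate has a smaller denominator and a wider interval, as in Step 5, and more so in subgroups. No patient leaves the all-patient ORR. Section 9.8 already provides for revising the eCRF after the pre-test and filing the revision with the IRB; including the item before the pre-test would avoid a separate resubmission.

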8. RESEARCH QUESTIONS AND OBJECTIVES

Limited data on durable responses in patients with *NRG1* gene fusion-positive solid tumors have been reported with afatinib. Beyond these data, no comprehensive evaluation has been conducted of patients harboring *NRG1* gene fusions treated with afatinib or other systemic therapy, in any line of therapy, to describe patient characteristics and clinical outcomes associated with afatinib use. This study aims to answer these questions by achieving the objectives stated below. As this study is descriptive in nature, no *a priori* hypothesis will be tested.

Research Questions:

1. What are the characteristics of patients with *NRG1* gene fusion-positive solid tumors treated with afatinib, and what are the characteristics of those treated with another systemic therapy?

Study Objectives:

1. To describe the demographic and clinical characteristics of patients with *NRG1* gene fusion-positive solid tumors treated with afatinib and of patients with *NRG1* gene fusion-positive solid tumors treated with other systemic therapy.
2. To calculate the ORR and DOR among patients with *NRG1* gene fusion-positive solid tumors treated with afatinib and among patients with *NRG1* gene fusion-positive solid tumors treated with other systemic therapy
3. To estimate PFS (and TOT, TTP) among patients with *NRG1* gene fusion-positive solid tumors treated with afatinib and among patients with *NRG1* gene fusions treated with other systemic therapy
4. To estimate OS among patients with *NRG1* gene fusion-positive solid tumors treated with afatinib and among patients with *NRG1* gene fusion-positive solid tumors treated with other systemic therapy
5. To describe the incidence and severity of AEs among patients with *NRG1* gene fusion-positive solid tumors while on treatment with afatinib or other systemic therapy

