9.8 QUALITY CONTROL

[REDACTED] will conduct all data quality assurance and control activities. The following sections outline the data quality assurance and control measures implemented throughout data collection, management, and inspection, prior to constructing a final analytic data file. These procedures are conducted from a programming standpoint (e.g., logic checks built into the data collection tool) via statistical analysis to identify patterns and outliers, and by clinical review to identify implausible data or incongruent data points on a given patient.

9.8.1 eCRF Functionality Testing

Prior to data collection and during the field test, [REDACTED] will test the eCRF. This quality control process begins with extensive testing of the eCRF to ensure functionality across web-based user environments, looping logic to ensure proper alignment of data-related fields (required responses to certain fields prior to entering data into subsequent field), and other programmatic checks to ensure the reduction of the input of erroneous data (such as specifying maximums for year of birth or initiation of treatment within the dates of the enrollment period). Only data ranges consistent with known clinical parameters will be allowed to be entered into the eCRF.

In addition, the eCRF will be field-tested among four providers to ensure its functionality, the correct interpretation of the questions in relation to the data points of interest, and the length of time required for completion for a single patient. Field-testing includes a [REDACTED] researcher viewing the screen of the provider completing the eCRF with actual patient data and asking probing questions regarding the functionality, interpretability (variables are aligned with clinical definitions or clinical interpretations), and availability of the variables requested. No data from the pre-testing phase will be used in the analysis for this research. Pre-testing of the eCRF will not commence until receiving IRB approval for the conduct of the study. The pre-test results will be reviewed by BI with [REDACTED] however, BI will not have access to the individual data collected. Any changes made to the eCRF document as a result of the pre-test will require the resubmission of the eCRF and study protocol to the IRB.

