10 PROTECTION OF HUMAN SUBJECTS

Individual patient medical information obtained as a result of this study is considered confidential and disclosure to third parties is prohibited. All study materials including the research protocol and paper-version of the eCRF will be reviewed by a central IRB prior to any data abstraction including field-testing of the eCRF. A waiver of HIPAA authorization for use of PHI will be requested from the IRB since the following three requirements will be met:

1. The use or disclosure of the PHI involves no more than minimal risk to the individuals, based on the following elements:
 - a. An adequate plan to protect identifiers from improper use and disclosure;
 - b. An adequate plan to destroy the identifiers at the earliest opportunity consistent with conduct of the research (unless there is a health or research justification for retaining the identifiers, or such retention is otherwise required by law); and
 - c. Adequate written assurances that the PHI will not be reused or redislosed to any other person or entity, except as required by law, for authorized oversight of the research project, or for other research for which the use or disclosure of PHI would be permitted by HIPAA.
2. The research could not be practicably conducted without access to and use of the PHI; and
3. The research could not practicably be conducted without the waiver.

Providers are required to be able to participate in research covered by a central IRB. At all times, patients' PHI will be kept confidential in accordance with HIPAA. The eCRF will not capture any data related to the patient's name, full date of birth, social security number, health insurance plan number, medical record number, or other such PHI. However, date of disease diagnosis, date(s) of treatment(s) administered (including dates of dose changes), date of the development of health states of interest (i.e., SAEs/FAEs, disease progression), and date of death (if available) will be collected in the eCRF. These items are considered PHI under HIPAA. All study results will be reported in aggregate; however, an anonymized patient-level dataset will be delivered to BI at the completion of the analytic cohort build.

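### Duration of response is defined only for patients in response at the first assessment, so the best-response ORR has no matching DOR

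*Combined protocol and SAP*

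**What the plan says.** Table 2 in Section 9.3.2 defines ORR as CR plus PR over all patients, "at initial response assessment and best response". Section 9.7 confirms that both versions are reported: the point estimate and 95% CI "will be calculated for initial response to index therapy (i.e., afatinib or other systemic therapy) and best response to index therapy, for each cohort".

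There is one DOR. Its Table 2 entry reads "Duration of response will be calculated as the time from initial response (for any patient with a complete or partial response initially", and it ends at progression or death. The neighbouring DOCB entry has the same start but a wider entry condition: "for any patient with a complete, partial, or stable disease response initially".

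Objective 2 in Section 8 ("To calculate the ORR and DOR among patients with") joins the two outcomes without saying which ORR the DOR accompanies. On data capture, Section 9.3.2 names imaging dates for the initial and the best response, and says of lesion measurements that those at baseline, "initial response, and best response will be abstracted as available".

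**The concern.** ORR and DOR are normally read together: how many patients respond, and for how long. Here the DOR set matches one of the two planned ORRs. A patient whose first assessment shows stable disease and who later reaches PR or CR is in the numerator of the best-response ORR but outside the DOR set.

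If DOR is printed beside the best-response ORR, it describes a smaller group selected on having responded by the first scan. Late responders may hold their responses for longer or shorter than early ones; the documents give no basis for either. Section 7 says the data may support label-expansion requests, so readers are likely to take DOR as the durability of whichever ORR is quoted.

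**Working it through.** The plan gives no figure for this point, so there is nothing to reproduce. The check is a comparison of definitions, followed by an illustration of scale.

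**1. What initial response means.** The term is not formally defined. It could be the result of the first assessment, or the first documented CR or PR. Three places favour the first assessment:
- The DOCB entry allows stable disease as an initial response, so the term there cannot mean first CR or PR.
- The ORR entry speaks of an initial response assessment.
- Section 9.7 uses initial response to index therapy for one of the two ORRs. If that meant first CR or PR, both ORRs would count the same patients and would be the same number.

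**2. Where each patient is counted, on that reading.**

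| First assessment | Best response | Initial ORR | Best ORR | DOR | DOCB, PFS, TTP |
|---|---|---|---|---|---|
| CR or PR | CR or PR | yes | yes | yes | yes |
| SD | CR or PR | no | yes | **no** | yes |
| SD | SD | no | no | no | yes |

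Nothing else restores the second row. DOCB starts at the stable-disease assessment, and PFS and TTP start with the line of therapy, so none measures time in response. The Section 9.7 rule on omitting patients whose outcome cannot be assessed concerns missing information; these patients are excluded by definition.

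**3. Number of responders without a DOR (illustration).** From the plan: up to 70 afatinib patients. Assumed: best-response ORR and the share *s* of responders with SD at the first assessment. DOR set = 70 × ORR × (1 − *s*).
- *s* = 1/3: ORR 20%, 30%, 40% gives 14, 21, 28 responders and a DOR set of 9.3, 14, 18.7.
- ORR 30% (21 responders): *s* = 20%, 1/3, 50% gives a DOR set of 16.8, 14, 10.5. Divided by 70, the initial-response ORR is 24%, 20%, 15% against 30%.
- If *s* = 0, nobody is lost.

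**4. Effect on median DOR (illustration).** Assumed: exponential durations with a median of 9 months in early responders and *m* months in late responders. The all-responder median *t* solves (1 − *s*)·exp(−ln2·*t*/9) + *s*·exp(−ln2·*t*/*m*) = 0.5.

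| *s* | *m* = 6 | *m* = 12 |
|---|---|---|
| 20% | 8.27 | 9.51 |
| 1/3 | 7.82 | 9.88 |
| 50% | 7.30 | 10.36 |

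The DOR as written would target 9.0 in every cell.

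**5. Sampling error for comparison.** The approximate 95% CI for an exponential median of 9 with *d* events is 9 × exp(±1.96/√*d*): 5.87 to 13.80 months for *d* = 21, and 5.33 to 15.20 for *d* = 14. With censoring, fewer events are seen and the intervals are wider.

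**The case against.** The strongest case against has four parts.

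- **The term is open.** The ORR entry says initial response assessment while the DOR entry says only initial response, so DOR could start at the first CR or PR with the two ORRs still distinct. This reading cannot be excluded outright. But Section 9.7 uses initial response for ORR as well, and the DOCB entry counts stable disease as an initial response. Even on this reading the term needs a definition, because two programmers could build different DOR sets.
- **The gap is visible.** The difference between the two ORR numerators is the number of responders without a DOR. That is right, but it does not supply their durations.
- **The impact is small.** The study is descriptive, tests no hypothesis, compares no cohorts and sets no threshold for DOR. The DOR as written is coherent with the initial-response ORR. All of this stands and limits the weight of the point.
- **The eCRF is not in the documents**, so it may already hold the date needed, and a start date based on measured lesions would also need measurements from that scan. The first part stands as a caution. However, Section 9.4 ties the form to the Section 9.3 variables, and Section 9.3.2 names imaging dates only for initial and best response. Section 9.3.2 also takes response for ORR from the patient's record, so a charted date of first CR or PR matches that source.

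**Conclusion.** The concern holds. As written, DOR accompanies the initial-response ORR only, and responders who began with stable disease have no DOR although they count in the best-response ORR. This rests on reading initial response as the first assessment, which the text favours but does not define.

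The consequence is one missing companion summary in a descriptive study. ORR, PFS and OS are unaffected. Under the assumed values, the set behind DOR falls from 21 to between about 10 and 17, and the median differs by about 0.5 to 1.7 months in either direction (9.51 − 9.0 at the least, 9.0 − 7.30 at the most). That is less than the sampling error, and the direction is unknown. The point should be corrected because the correction is cheap before data collection and harder afterwards.

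**What to change.** 1. In Table 2, define DOR for every patient with CR or PR as best response, from the first imaging that documents CR or PR to progression or death, and pair it with the best-response ORR.
2. Keep the DOR in initial responders as a labelled summary paired with the initial-response ORR.
3. Define initial response in Table 2 as the first response assessment, if that is what is meant, and state in objective 2 which ORR each DOR accompanies.
4. Unless the eCRF already has it, add one field for the date of first documented CR or PR. For a patient who goes from SD to PR to CR, the initial and best-response dates do not give this date, and starting at the best-response date would make DOR too short.

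The cost is a short text edit, one more reported summary and a little extra abstraction per responder. The field should be in the form before the IRB review planned for July 2020 (Section 6). Section 10 states: "All study materials including the research protocol and paper-version of the eCRF will be reviewed by a central IRB prior to any data abstraction". Under Section 9.8.1, any eCRF change arising from the pre-test "will require the resubmission of the eCRF and study protocol to the IRB".
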